### 8.3 Plans for return of research results

All data collected as part of this study will be for research purposes only and subjects will be explicitly told that the experiment will not provide information as to their health status. At the end of the study, after all data have been collected and analyzed, we will post a link to our study findings on our lab website for participants to see.

## 9. Risks to subjects

### 9.1 Risks to subjects and adequacy of protection against risk

#### 9.1.1 Weight loss due to the intervention

Some studies have documented weight loss upon adoption of the Mediterranean Diet despite consuming calories *ad libitum*. Our intervention diet will be *ad libitum* and participants will be encouraged to satisfy thirst and hunger. However, due to the satiating nature of the Mediterranean Diet compared to the typical Western diet, and the fact that they are initiating chemotherapy, there is a chance that patients could enter a calorie deficit and lose weight during the course of the intervention. If the patient is overweight or obese, slow weight loss will not be considered an adverse event (less than approximately 3% of their body weight per week). Weight measured from clinical visits will be recorded by study staff and used to assess rapid weight loss. If a patient experiences rapid, unintentional weight loss, as monitored and determined by the treating oncologist, the physician will determine how to intervene. It is important to determine what is causing the weight loss. If it is suspected that the study meals are contributing, the physician could recommend:

- Reviewing food records to see if there are any new foods that the patient is consuming from the intervention diet that they could have an unexpected reaction to; for example, there could be an ingredient to which the participant has an intolerance, leading to nausea and/or diarrhea and contributing to the weight loss,
- Discontinuing consumption of all study-related foods, and/or
- Other relevant actions on the patient-level.

Rapid, unintentional weight loss could be a symptom of another underlying condition, such as the onset of diabetes, cachexia, etc. If it is determined that the study foods are not contributing to the weight loss, the physician will decide if it is safe for the patient to continue with the study. We will follow the Common Terminology Criteria for Adverse Events (CTCAE), version 5, to record weight loss as an adverse event:

- Weight loss 5 – <10% from baseline with no intervention indicated will be considered a Grade 1 adverse event.
- Weight loss of 10 – <20% from baseline and indicated nutritional support will be considered a Grade 2 adverse event.
- Weight loss  $\geq 20\%$  from baseline with indicated tube feeding or total parenteral nutrition will be considered a Grade 3 adverse event.

We will follow the treatment team and registered dietitians' recommendations for nutritional interventions due to any weight loss.

Weight loss can cause anxiety in patients with cancer. However, knowing that this dietary intervention usually results in weight loss, particularly in people who are overweight, can be reassuring in that weight loss is due to dietary change and not a manifestation of progressive cancer, particularly if there are no other concerning symptoms.

Probability: High probability that some weight loss will be experienced, especially in patients with excess body fat; low probability that a dangerous amount of weight will be lost

Magnitude: Weight loss can range from low to high, or weight gain can occur

Duration: Short- to long-term

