### **4. Study design**

#### *4.1 Brief description and specific aims*

This will be a feasibility pilot randomized controlled trial performed at a single site. We will recruit 42 patients with cancer who are beginning a chemotherapy regimen and randomize them 2:1 to the intervention group or usual care (28 in the intervention arm and 14 in the usual care arm). The uneven allocation serves to improve recruitment, as some patients are disappointed to be assigned to the usual care arm, and allows us to get more information about the intervention. This will be an open label study (due to the nature of the intervention it is not possible to blind participants, and due to the active involvement of the PI in data acquisition, it is not feasible to blind the PI). At baseline, participants will complete an on-study form that includes demographics and clinical characteristics. They will complete a 3-day food record (ideally from two weekdays and one weekend day), a fasted blood draw, and several questionnaires [i.e., 14-Item Mediterranean Diet Assessment Tool, Functional Assessment of Chronic Illness Therapy – Fatigue (FACIT-F), Aerobics Center Longitudinal Study (ACLS) physical activity questionnaire, Brief Fatigue Inventory (BFI), 27-item Symptom Inventory, Functional Assessment of Cancer Therapy-Cognition (FACT-Cog), Brief Pain Inventory (BPI), Insomnia Severity Index (ISI)]. For the duration of the study, all participants will complete a daily diary that includes their average fatigue level that day. For 4 weeks, we will provide participants in the intervention group with food based on the Mediterranean Diet. We intend this food to be substituted or supplemented with other food of the patients' choosing, though we encourage participants to comply with the Mediterranean Diet for all meals and snacks. During this time we will also provide education regarding the principles and composition of the Mediterranean Diet and how to effectively implement it at home. This education will include materials that encourage behavior change to inspire motivation and adherence to the diet. At 4 weeks, participants will undergo a mid-point evaluation where they will complete the same assessments as at baseline except for the on-study form. For weeks 5-8, participants in the intervention group will be encouraged to follow the Mediterranean Diet though we will not provide food. During the 8-week intervention, we will be in contact with participants in both groups to monitor adverse events and discuss any barriers to consuming the diet (in the intervention group). At 8 weeks, participants will repeat the assessments and undergo an exit interview, which will last approximately 15-30 min. Participants will receive \$20 total to complete baseline and post-intervention measures and those in the intervention group will receive free meals for 4 weeks. Those in the usual care group will be offered the intervention materials and one week of meals *gratis* at the conclusion of the study.

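### Section 9.1.1 exempts slow weight loss in overweight or obese participants without a cumulative limit, yet grades 5 to <10% loss from baseline as an adverse event; the two recording rules conflict at Grade 1

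*Combined protocol and SAP*

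**What the plan says.** Section 9.1.1 gives two rules for recording weight loss.

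- **Weekly-rate rule, overweight or obese participants only:** "slow weight loss will not be considered an adverse event (less than approximately 3% of their body weight per week". No ceiling on the accumulated loss is given.
- **Cumulative rule, no subgroup named:** CTCAE version 5 is to be used to record weight loss as an adverse event. A loss of 5 to <10% "from baseline with no intervention indicated will be considered a Grade 1 adverse event". A loss of 10 to <20% "from baseline and indicated nutritional support will be considered a Grade 2 adverse event". A loss of 20% or more "from baseline with indicated tube feeding or total parenteral nutrition will be considered a Grade 3 adverse event".

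The section also covers care. For rapid, unintentional loss, "as monitored and determined by the treating oncologist, the physician will determine how to intervene". The team will follow the treatment team's and dietitians' "recommendations for nutritional interventions due to any weight loss". Weights from clinic visits are recorded by study staff. The stated expectation is: "High probability that some weight loss will be experienced, especially in patients with excess body fat".

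On monitoring and reporting:

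- Section 4.1 says "we will be in contact with participants in both groups to monitor adverse events".
- Section 16.1 defines an adverse event broadly, to include any sign that appears or worsens on study whatever its cause. It gives grading and attribution to the referring oncologist, a designee or the medical monitor. Weight loss goes to the RSRB only if it meets the general reporting criteria.
- Section 16.2 sends the adverse event spreadsheet to the DSMC with the progress report. It lists the review content as enrolment, withdrawals and serious adverse events.

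**The concern.** One rule works on weekly rate and the other on cumulative loss from baseline. An overweight participant who loses weight slowly but steadily can satisfy both: not an adverse event under the first, Grade 1 under the second. Sections 9.1.1, 16.1 and 16.2 contain no sentence that ranks them.

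What is at stake is the safety record. The choice of rule decides whether the loss appears on the spreadsheet that goes to the DSMC, and two people could log the same participant differently. The exempted group is the one in which the plan most expects weight to fall. The trial is also open label, and under section 8.2.5 the principal investigator takes part in intervention delivery, data acquisition and analysis, so the recording rule should not be left to choice.

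**Working it through.** The plan states no figure on this point that could be reproduced. The check is whether the two rules can apply to the same participant within the study, and at which grade.

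**Inputs**

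- Exemption: below about 3% of body weight per week, overweight or obese (9.1.1).
- Grade thresholds: 5%, 10% and 20% from baseline (9.1.1).
- Time over which loss accumulates: 8 weeks on study (8.2.6).
- Assumption: a constant weekly rate *r*. The plan gives no expected rate.

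**Formulas**

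- Cumulative loss after *w* weeks = 1 − (1 − *r*)^*w*.
- Rate that reaches loss *L* at week 8 = 1 − (1 − *L*)^(1/8).
- Week at which loss *L* is reached = ln(1 − *L*) / ln(1 − *r*).

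**Step 1: the range of overlap.** The rate that just reaches 5% at week 8 is 1 − 0.95^(1/8) = 0.64% per week. The rate that just reaches 10% is 1 − 0.90^(1/8) = 1.31% per week. If the rate is taken as a fixed share of baseline weight instead, these become 5/8 = 0.625% and 10/8 = 1.25%. So every constant rate from about 0.64% to just under 3% is exempt and also reaches 5% by week 8. Rates from 0.64% to just under 1.31% end the study inside the Grade 1 band; faster exempt rates pass through it earlier.

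**Step 2: examples, all exempt under the weekly rule**

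| Weekly rate | Reaches 5% | Reaches 10% | Loss at week 8 |
|---|---|---|---|
| 1% | ln 0.95 / ln 0.99 = week 5.1 | not by week 8 | 1 − 0.99^8 = 7.7% |
| 2% | week 2.5 | week 5.2 | 1 − 0.98^8 = 14.9% |
| 2.9% | week 1.7 | week 3.6 | 1 − 0.971^8 = 21.0% |

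The corresponding linear totals at week 8 are 8.0%, 16.0% and 23.2%.

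**Step 3: at which grade the rules collide.** Grade 1 needs a loss of 5 to <10% and no intervention indicated, which is the ordinary situation for a slow, welcome loss. Nothing further has to happen for both rules to apply. Grade 2 also needs nutritional support to be indicated, and Grade 3 needs tube feeding or total parenteral nutrition to be indicated. The unconditional conflict is therefore at Grade 1.

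**Step 4: a gap in the grade list.** As worded in 9.1.1, a loss of 10% or more without indicated nutritional support meets none of the three grades. This is separate from the exemption, but a fix has to cover it.

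**The case against.** The best defence is that the first rule is a deliberate exception. It decides whether a loss counts as an adverse event in one named subgroup, and the CTCAE list then grades whatever does count. Section 16.1 gives CTCAE that severity role, and 9.1.1 expects weight loss in overweight people and treats it as potentially reassuring. A specific rule beside a general scale is ordinary drafting. This reading is coherent, but the text does not state it: the CTCAE list is introduced as the way to record weight loss as an adverse event, with no subgroup left out. Followed literally, the reading also leaves the exemption without a cap during chemotherapy.

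Several other objections stand in whole or in part:

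- Sustained losses of 2% to 2.9% per week are hypothetical. Intake is unrestricted, participants are encouraged to satisfy hunger, and the plan rates a dangerous loss as unlikely.
- Clinic weights are recorded under either rule, so an unlogged loss could be recovered later.
- Section 16.1 names who grades events, which reduces the risk of inconsistent logging. It does not tell them which rule to use.
- A statement of precedence in either direction would remove the ambiguity. Choosing 5% as the limit narrows the sponsor's exemption, so it is a judgement.

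A reader might infer that the exemption lets losses of 15% to 21% go unnoticed or untreated. The documents do not support this. The treating oncologist determines rapid loss, with no dependence on the 3% figure, and dietitian advice is followed for any loss. Nor can missing grades at those levels be put down to the exemption alone, because without indicated support the CTCAE list gives them no grade either.

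**Conclusion.** Wrong as written, minor severity. For overweight or obese participants, section 9.1.1 gives opposite answers on whether a slow loss of 5 to <10% from baseline is an adverse event, and no other section settles it. Under a constant weekly rate, the overlap runs from about 0.64% to just under 3% per week. The 14.9% and 21.0% totals only illustrate that the exemption has no cap; they are not forecasts.

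The number of participants affected cannot be estimated, because the plan gives neither an expected rate of loss nor the expected share of overweight participants among the 42. The consequence is confined to the adverse event spreadsheet. A Grade 1 entry would not go to the RSRB, and the DSMC review content listed in 16.2 names serious events only. Feasibility, the FACIT-F analysis and the sample size are untouched.

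Confidence is high that the conflict exists. It would be wrong to go further and call this a gap in patient care.

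**What to change.** Replace the exemption sentence in 9.1.1 with wording such as:

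> In overweight or obese participants, loss below approximately 3% of body weight per week is not recorded as an adverse event while cumulative loss from baseline is under 5%. At 5% or more from baseline, the loss is recorded as an adverse event in all participants in both arms, whatever their body weight or weekly rate, and graded by the CTCAE list below. Loss of 10% or more without indicated nutritional support is recorded as at least Grade 1.

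The last sentence closes the gap in the list, so that larger losses are not left ungraded. Grade and attribution stay with the roles in 16.1. The determination of rapid loss stays with the treating oncologist, and 3% per week should not become a trigger for action.

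The change uses clinic weights already recorded and needs no new visit or measurement. Its cost is a few more low-grade entries, some of them for weight loss that the participant and clinician welcome.

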Either [name] (study chair) or a member of the study staff who was trained by [name] will deliver the intervention. The intervention will be standardized and include a checklist for the interventionist to ensure fidelity of the intervention and to prevent drift. For interventions delivered by a staff member other than [name], at least one out of five sessions will be either attended by [name] or audio-recorded; feedback will be provided to the interventionist.

We will contact participants once a week so that we can check in, assess adverse events, and troubleshoot any issues with compliance.

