### 8.2.7 Schedule of assessments

Baseline assessments will optimally be collected before the first infusion of chemotherapy, though assessments will not delay chemotherapy. Baseline assessments after chemotherapy is initiated is permissible as long as the patient has at least 6 more weeks of chemotherapy. 4-Week assessments will occur approximately during week 4 (during week 3-5); 8-week assessments will occur approximately during week 8, the last week of the intervention (week 7-9). However, this may be adjusted to accommodate factors such as the participant or researcher's schedule. Because of the immediate and transient effects that chemotherapy has on fatigue, we will aim to have assessments at least 3 days after an infusion. Optimally, the post-intervention assessments will occur during the last week of the intervention, while the participant is still on the diet, so that we can probe metabolic markers that may change quickly after cessation of the diet. **Table 3** describes two common chemotherapy regimens, but others exist and we will work around clinic activities to collect assessments.

Study Week	0	1	2	3	4	5	6	7	8
Study activities	Consent, Baseline assessments				4-week assessments				8-week assessments
Infusion number (for patients on biweekly regimens)		1		2		3		4	
Infusion number (for patients on weekly regimens)		1	2	3	4	5	6	7	8
Infusion number (for patients on an every 4-week regimen)		1				2			
Infusion number (for patients on an every 3-week regimen)		1			2			3	

**Table 3.** Schedule of chemotherapy infusions and study activities for two example chemotherapy regimens.

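### Section 9.1.1 uses a per-week weight-loss figure, but no weighing interval is set and no weight is scheduled at baseline, week 4 or week 8

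*Combined protocol and SAP*

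**What the plan says.** Section 9.1.1 treats weight loss as an expected effect of the diet: "High probability that some weight loss will be experienced", especially with excess body fat, although it rates a dangerous loss as improbable. It then gives three separate rules.

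- An exemption by rate: "If the patient is overweight or obese, slow weight loss will not be considered an adverse event", where slow means "less than approximately 3% of their body weight per week".
- A clinical judgement: the response is triggered by "rapid, unintentional weight loss, as monitored and determined by the treating oncologist". No number is attached to rapid.
- CTCAE version 5 bands for loss from baseline: 5 to <10%, 10 to <20%, and 20% or more, with no reference to elapsed time. Each band is also tied to the nutritional intervention indicated.

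The data source is given in one sentence: "Weight measured from clinical visits will be recorded by study staff and used to assess rapid weight loss". Section 8.2.2 lists weight among the items in the Clinical Record, without dates. Table 4 (section 8.2.8) has no weight row. Table 3 (section 8.2.7) shows infusions for example regimens. Between visits, section 4.3.1 says: "We will contact participants once a week so that we can check in, assess adverse events, and troubleshoot any issues with compliance". Weight is not mentioned there or in section 14.3. Section 16.1 nevertheless promises close monitoring of weight loss.

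**The concern.** A rate per week can be calculated only over a known interval, and the plan fixes neither the interval nor the dates of the weights. If weights are several weeks apart, a short, fast loss is spread over the whole gap and can look slow. The from-baseline bands need a baseline weight and at least one later weight, and neither is scheduled.

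Three things are at stake. Monitoring of a risk the protocol itself expects would depend on the chemotherapy regimen. Weeks 5-8, when food is no longer provided, could lack a measured weight for some participants. And a pilot meant to inform a larger trial would have no weight change by arm on common dates.

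**Working it through.** The plan states no calculated figure on this point, so there is none to reproduce. The check is whether the weights it provides for can support its own weekly rate.

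**Inputs.** Weekly rate of about 3% and CTCAE bands from 5%, 10% and 20% (section 9.1.1); infusion weeks (Table 3); blood draws at baseline, week 4 and week 8 (Table 4); eligibility of a patient whose last infusion is 6 weeks away (section 5).

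**Assumptions.** Weights are taken only at infusion visits, exactly in the Table 3 weeks; the participant is at baseline weight before the loss; averaging is linear unless marked compound.

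**Step 1: gaps and apparent rate.** Apparent rate = loss / gap. Loss needed to average 3% per week = 3 × gap (linear) or 1 − 0.97^gap (compound).

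| Regimen | Infusion weeks | Largest gap (weeks) | A 4% one-week loss reads as | Loss needed to average 3% per week (linear; compound) | Weeks from last infusion to week 8 |
|---|---|---|---|---|---|
| Weekly | 1 to 8 | 1 | 4/1 = 4.0% per week | 3%; 3.0% | 0 |
| Every 2 weeks | 1, 3, 5, 7 | 2 | 4/2 = 2.0% | 6%; 5.9% | 1 |
| Every 3 weeks | 1, 4, 7 | 3 | 4/3 = 1.3% | 9%; 8.7% | 1 |
| Every 4 weeks | 1, 5 | 4 | 4/4 = 1.0% | 12%; 11.5% | 3 |

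A 4% loss is also below the 5% band, so on the longer regimens it meets neither numeric criterion. On weekly weights it would exceed the 3% figure.

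**Step 2: late weeks.** Every-4-week regimens: 8 − 5 = 3 weeks after the last infusion shown. A participant whose last infusion is at week 6: 8 − 6 = 2 weeks.

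**Step 3: sensitivity to the blood draws.** If weight were also taken at weeks 0, 4 and 8, an every-4-week participant would have weights at 0, 1, 4, 5 and 8, and the largest gap falls from 4 to 3 weeks. An every-3-week participant would have 0, 1, 4, 7 and 8, and the largest gap stays at 3. The plan does not say that weight is taken at the draws. Sections 4.4.3 and 8.2.4 allow them at a laboratory service center, and section 13 lets participants skip any assessment.

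**Step 4: the two numeric rules side by side.** A steady 2.9% per week is slow under the exemption. Over 4 weeks it totals 2.9 × 4 = 11.6% (linear) or 1 − 0.971^4 = 11.1% (compound), which is inside the 10 to <20% range. For an overweight participant, section 9.1.1 therefore points both ways and gives no order of precedence.

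**The case against.** The strongest reply is that section 9.1.1 does not rely on the weekly figure to detect harm. A reader might infer that 3% per week is the protocol's test for rapid loss. It is not: it only removes slow loss from adverse-event status, and only in overweight or obese participants. Rapid loss is left to the treating oncologist. That stands, although clinic weights are what the section says will be used to assess it, so their spacing still matters.

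A reader might also infer that fast losses are simply averaged away. For 5% or more this is not supported: the from-baseline bands ignore time, so such a loss falls in a band at the next weight, unless the exemption overrides it. Nor is the 11% figure in Step 4 caused by sparse weighing; weekly weights would show the same steady loss. It shows only that the two rules conflict.

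Nor do the documents establish that clinic visits are up to 4 weeks apart or that late losses go unseen. Table 3 lists infusions for example regimens, not all visits. Sections 4.4.3 and 6.1.1 mention routine medical blood draws and oncology appointments. Weekly contact runs through week 8 and could pick up a reported loss. Table 4 lists participant activities, so a chart-derived weight need not appear there.

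All of this narrows the point. None of it supplies a weighing interval, a scheduled baseline, week 4 or week 8 weight, or an order of precedence between the rules.

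**Conclusion.** The point holds as a modest gap in safety measurement. The plan pairs a per-week figure with weights that have no set interval or dates. If weights come only from infusion visits, a 4% one-week loss can read as 1.3% (every 3 weeks) or 1.0% (every 4 weeks) per week and stay under the 5% band. Every-4-week participants, or those finishing infusions by about week 6, may have no measured weight for the last 3 or 2 weeks. This is a possibility, not a certainty: extra oncology visits would shrink the gaps, and weekly or every-2-week regimens are affected little or less.

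Separately, section 9.1.1 contradicts itself for overweight or obese participants who lose weight steadily at just under the exempt rate, and its rules must be reconciled. The documents do not support the stronger claim that the plan will miss dangerous losses. The change is worth making because it is cheap and concerns a risk the protocol itself expects.

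**What to change.** - Add a body-weight row to Table 4 at baseline, week 4 and week 8 in both arms: clinic-measured where possible, otherwise self-reported and marked as such, with the date.
- State in section 9.1.1 the interval over which the weekly rate is calculated. The three added weights alone do not do this, since gaps of 3 weeks remain (Step 3).
- Have the investigators state whether the CTCAE bands or the overweight/obese exemption prevails when both apply.
- Tabulate percent weight change from baseline by arm at weeks 4 and 8.

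Thresholds, escalation and clinical response stay with the investigators. Weekly self-weighing is not proposed: Table 2 lists self-monitoring as a behavior-change strategy, so asking for it in both arms could itself alter behavior.

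Cost: one table row, two clarifying sentences and one summary table, with no new visit. The downside is that some weights will be self-reported and less accurate.
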